**A NON-RANDOMIZED, CONSECUTIVE ENROLLMENT EVALUATION OF THE
DESolve® NOVOLIMUS ELUTING BIORESORBABLE CORONARY SCAFFOLD
SYSTEM IN THE TREATMENT OF PATIENTS WITH *DE NOVO* NATIVE
CORONARY ARTERY LESIONS**

**Elixir Medical Clinical Evaluation of the DESolve® Novolimus Eluting Bioresorbable
Coronary Scaffold System**

“DESolve Nx Trial – DESolve CX Arm”

Revision E, 5 February 2018

Brazil

NCT04034121

CLINICAL STUDY SUMMARY

Trial Name and Number	DESolve Nx Trial: ELX-CL-1003
Objectives:	To evaluate the safety, performance and efficacy of the Elixir DESolve [®] Novolimus Eluting Bioresorbable Coronary Scaffold System (BCSS) in patients with a single de novo native coronary artery lesion designated the target lesion and up to one non-target lesion located in a separate epicardial vessel.
Enrollment:	The study is designed to enroll 120 non-randomized patients with a single de novo native coronary artery lesion designated the target lesion and up to one non-target lesion located in a separate epicardial vessel. The target lesion must measure between 2.75 mm and 3.5 mm in diameter and ≤ 10 mm or ≤ 14 mm in length able to be covered by a single 3.0 x 14, 3.0 x 18mm, 3.25 x 14 or 3.25 x 18 mm, 3.5 x 14 mm or 3.5 x 18 mm DESolve scaffold. As applicable, a non-target lesion located in a separate epicardial vessel must be treated first with a single, approved ‘olimus drug eluting stent and if this procedure is uncomplicated and considered optimal, then the target lesion can be considered for the DESolve Novolimus Eluting BCSS. The patient should not be enrolled until after satisfactory pre-dilatation of the target lesion. Enrollment and follow-up is complete.
	The Low Profile 1 study arm is designed to enroll 100 non-randomized patients with a single de novo native coronary artery lesion designated the target lesion and up to one non-target lesion located in a separate epicardial vessel. The target lesion must measure between 2.75 mm and 3.5 mm in diameter and ≤ 10 mm or ≤ 24 mm in length able to be covered by a single 3.0, 3.25 or 3.5 mm x 14, 18 or 28 mm scaffold. This device differs only in the thickness of the scaffold which is now 100-120 μm as compared to the 150 μm of the device previously studied and shown safe and effective. As applicable, a non-target lesion located in a separate epicardial vessel must be treated first with a single, approved ‘olimus drug eluting stent and if this procedure is uncomplicated and considered optimal, then the target lesion can be considered for the DESolve Novolimus Eluting BCSS. The patient should not be enrolled until after satisfactory pre-dilatation of the target lesion. Patients included in this

	Arm will be enrolled at select sites. Follow-up will conclude at the end of 3 years.
Clinical Study Device	
3.0 x 14 mm, 3.0 x 18 mm, and 3.0 x 28mm; 3.25 x 14 mm, 3.25 x 18 mm and 3.25 x 28 mm; 3.5 x 14mm, 3.5 x 18 mm and 3.5 x 28 mm DESolve scaffolds
 
All DESolve scaffolds are loaded with approximately 5 mcg of Novolimus per mm of scaffold length (i.e, 65 mcg on a 14 mm scaffold, 85 mcg on an 18 mm scaffold and 125 mcg on a 28 mm scaffold).

Clinical Site Locations:	Drawn from up to 15 International Sites in Brazil, Belgium, Denmark, Germany, Poland and New Zealand
Clinical Study Design	
The DESolve Nx Trial is a prospective, consecutive enrolment non-randomized study designed to enroll patients with a de novo lesion \leq 14 mm in length, designated the target lesion, located in a native coronary artery with a reference vessel diameter of 2.75 mm – 3.5 mm. All patients will receive a 3.0, 3.25 or 3.5 mm x 14, 18 or 28 mm scaffold. DESolve scaffold loaded with approximately 5 mcg of Novolimus per mm of scaffold length. As appropriate, a non-target lesion may be treated in a separate native epicardial vessel with a single, approved ‘olimus drug eluting stent. Only the target vessel will be evaluated for the key safety and efficacy endpoints.
 
Multiple registry arms are to be included in the study with patients to be enrolled at select sites:
 
 • Low Profile 1 – a lower profile (thinner) scaffold (100-120μm) with the same drug dose 
To provide an assessment of the lesion and scaffold morphology and scaffold strut composition over time, the following additional imaging modalities will be included:
 
 • Angiography will be completed at 6 months following the index procedure in all patients. • In a subset of the first 35 patients enrolled at select sites, IVUS and OCT will be conducted at 6 and 24 and/or 36 months following the index procedure. These patients will also undergo angiography during the 24 and/or 36 month follow-up.

	
 • Multislice computed tomography (MSCT) will be conducted at 12 months in the subset of the first 35 patients enrolled at select sites. • All main trial patients will undergo clinical follow-up at 1, 6, and 12 months and annually through 5 years. • LP1 patients will undergo clinical follow-up at 1, 6, and 12 months and annually through 3 years
Clinical Endpoints:	
 • Clinically-indicated Major Adverse Cardiac Events (MACE) at 1, 6, and 12 months and annually to 5 years for all main study patients and for Low Profile 1 (LP1) patients at 1, 6, and 12 months and annually through 3 years. MACE is a composite endpoint defined as cardiac death, target vessel MI, and clinically-indicated target lesion revascularization • Acute Success including Device and Procedure Success • Clinically-indicated Target Lesion and Target Vessel Revascularization (CI-TLR and CI-TVR) at 1, 6, and 12 months and annually to 5 years for all main study patients and for LP1 patients at 1, 6, and 12 months and annually through 3 years • Clinically-indicated Target Lesion and Target Vessel Failure (CI-TLF and CI-TVF) at 1, 6, and 12 months and annually to 5 years for all main study patients and for LP1 patients at 1, 6, and 12 months and annually through 3 years • Scaffold Thrombosis at 1, 6, and 12 months and annually to 5 years for all main study patients and for LP1 patients at 1, 6, and 12 months and annually through 3 years
Angiographic Endpoints:	
All patients will undergo angiographic follow-up at 6 months. In a subset of the first 35 patients enrolled at select sites angiography will also be conducted at 24 and/or 36 months.
 
The following endpoints will be analyzed:
 
 • In-scaffold late lumen loss • In-scaffold and in-lesion Binary Restenosis ($\geq 50\%$) • In-lesion Late Lumen Loss

	
 • In-scaffold and in-segment % Diameter Stenosis • MLD and % DS post procedure • Scaffold Thrombosis • Additional parameters may be assessed
IVUS and OCT Endpoints	
To provide an assessment of the lesion and stent morphology and stent strut composition over time, the additional imaging modalities of IVUS and OCT conducted at baseline, 6 and 24 and/or 36 months will be completed in a subset of the first 35 patients enrolled at select sites. The following endpoints will be analyzed:
 
 • Volumetric neointimal burden by IVUS • Changes in vessel size by IVUS • Changes in scaffold size by IVUS • Changes in strut appearance suggesting bioresorption • Incomplete scaffold apposition, acute and late, assessed by IVUS and/or Optical Coherence Tomography (OCT) • Scaffold area assessed by IVUS and/or OCT • Descriptive analysis of lesion/vessel morphometry and scaffold strut composition by OCT
MSCT Analysis Endpoint	
In a subset of the first 35 patients enrolled at select sites, MSCT follow-up will be conducted at 12 months. The following endpoints will be analyzed:
 
 • Multi-slice computed tomography (MSCT) descriptive and quantitative analysis of lesion/vessel and scaffold morphology
Treatment Strategy	
 • Treatment of up to two de novo native coronary artery lesions located in separate epicardial territories. One will be the target lesion and will be treated with the trial device.

- Treatment of the target lesion is to be performed after optimal stenting using an approved 'olimus DES of a single non-target lesion as applicable.
- To determine patient eligibility, assessment of the target vessel diameter using on-line QCA must be completed before the enrollment of the patient into the study. The target lesion is to be treated only after all clinical and angiographic inclusion criteria have been met
- Pre-dilatation of the lesion is mandatory using a balloon approximately sized to the reference vessel. If the lesion cannot be successfully pre-dilated, treatment with the DESolve CSS should not be attempted. If there is Type A dissection that cannot be covered by the DESolve CSS then the patient cannot be enrolled in the trial. Any dissection worse than Type A will preclude the patient from being enrolled into the study.
- Target lesion length should be ≤ 10 mm or ≤ 24 mm by visual estimate and have at least 2 mm of healthy vessel on either side of the lesion for coverage by the DESolve Scaffold

Table 1: Lesion length, Scaffold size and Drug dose

Lesion length (visual estimation)	DESolve Stent size	Drug dose
≤ 10 mm	3.0 x 14 mm	65 mcg
	3.25 x 14 mm	
	3.5 x 14 mm	
≤ 14 mm	3.0 x 18 mm	85 mcg
	3.25 x 18 mm	
	3.5 x 18 mm	
≤ 24 mm	3.0 x 28 mm	125 mcg
	3.25 x 28 mm	
	3.5 x 28 mm	

	
 • Bailout stenting should be conducted using any approved DES stent incorporating an “olimus” drug or bare metal stent • Patients should receive a loading dose of clopidogrel (≥ 300 mg) and aspirin (≥ 300 mg) if not currently on chronic anti-platelet therapy 24 hrs prior to the index procedure. Patients should remain on 75mg of clopidogrel daily for at least 12 months and on ≥ 75 mg of aspirin indefinitely or at least for the length of the study follow-up period of 5 years. • All patients will undergo angiography at the 6 month follow-up. • IVUS and OCT will be conducted at baseline, 6 and 24 and/or 36 months in a subset of the first 35 patients enrolled at select sites. This subset of patients will also undergo angiography at the 24 and/or 36 month follow-up. • Multislice computed tomography (MSCT) will be conducted will be conducted at 12 months in the subset of the first 35 patients enrolled at select sites.

Key Inclusion Criteria
	
Patients have a planned intervention of up to two native coronary artery lesions located in separate epicardial territories, one designated the target lesion and the other a non-target lesion, which meet the following criteria:
 
The non-target lesion must be treated first using a single, approved ‘olimus drug eluting stent. If uncomplicated and considered optimal as defined by below, the target lesion can then be treated.
 
Optimal treatment of non-target lesion:
 
 a. $< 20\%$ residual stenosis by visual assessment b. no evidence of dissection c. no evidence of thrombus in the target lesion or vessel d. TIMI 3 flow 
No other restrictions are placed on the non-target lesion. The patient and target lesion must meet all patient inclusion criteria and no exclusion criteria.
 
Target Lesion inclusion criteria:

	
 • de novo • The target lesion reference site must be between ≥ 2.75 mm and ≤ 3.5 mm in diameter assessed by online QCA • The target vessel must be a major coronary artery or major branch with a visually estimated stenosis of $\geq 50\%$ and $<100\%$ with TIMI flow of ≥ 1 • The visually estimated target lesion length is ≤ 10mm or ≤ 14 mm and must be able to be covered by a single 14 mm or 18 mm DESolve® Scaffold • Percutaneous intervention of lesions in a non-target vessel if: 
 ○ Not part of a another clinical investigation ○ ≥ 30 days prior to the study index procedure ○ ≥ 9 months after the study index procedure (planned) ○ Treatment of a single, non-target lesion located in a separate major epicardial vessel (defined as LAD with septal and diagonal branches, LCX with obtuse marginal and/or ramus intermedius branches and RCA and any of its branches) attempted during the index procedure must be completed first using an approved ‘olimus drug eluting stent. If the procedure is deemed uncomplicated and optimal, treatment of the target lesion with the DESolve scaffold can be considered. • Percutaneous intervention of lesions in the target vessel if: 
 ○ Not part of a clinical investigation ○ ≥ 6 months prior to the study index procedure ○ ≥ 9 months after the study index procedure (planned) ○ Previous intervention was distal to and >10mm from the target lesion • The patient must be an acceptable candidate for coronary artery bypass surgery
--	--


Key Exclusion Criteria
	
Patients must not have any of the following:
 
 • An untreated significant lesion of > 40% diameter stenosis remaining proximal or distal to the target site after the planned intervention • The lesion is aorto-ostial in location, an unprotected left main lesion, a lesion within 5 mm of the origin of the LAD or LCX, or involves a major side branch < 2mm in diameter • Previous placement of a stent proximal to or within 10 mm of the target lesion • Total occlusion or < TIMI 1 coronary flow in the target vessel • The proximal target vessel or target lesion contains thrombus, moderate to severe calcification or exhibits severe tortuosity ($\geq 45^\circ$ angulation) by visual assessment • High probability that treatment other than PTCA or stenting will be required for treatment of the same lesion • Patient is a woman of childbearing potential, pregnant or nursing • Patient has received brachytherapy in an epicardial vessel • Any use of rotablator at the index procedure • The patient was diagnosed with an acute myocardial infarction (AMI) within the past 72 hours and the CK and CKMB have not returned to normal and the patient is experiencing clinical symptoms indicative of ongoing ischemia

Statistical Analysis
	
Analysis Populations in this observational study.
 
Modified-Intent-to-Treat Evaluable Population
 
The modified-intent-to-treat evaluable population will consist of patients who have received the investigational device at the target lesion, who have no major procedural protocol deviations (e.g. scaffold implanted in a non-native coronary artery), no bailout scaffolding and for whom follow-up data is available.

	
Intent-to-Treat Population
 
The intent-to-treat population will consist of all patients enrolled in the study, regardless of the treatment actually received for the target lesion.
 
Statistical Analyses
 
Detailed descriptive analyses of endpoints will be performed after each follow-up time point. No effort will be made to impute or extrapolate data to replace missing values. All calculations will be based on available data with missing data excluded. Any unused or spurious data will be noted as appropriate in the final report.
 
All clinical, angiographic, IVUS and OCT endpoints will be analyzed for the modified-intent-to-treat evaluable population. Descriptive statistics will be presented.
 
For binary variables such as MACE, ABR, TLR, TVF, and persistent incomplete apposition of the scaffold, counts, percentages, and exact 95% confidence intervals using Clopper-Pearson’s method will be calculated.
 
For continuous variables, means, standard deviations, and 95% confidence intervals for the mean using the Gaussian approximation will be calculated. If the assumption of normality seems untenable, nonparametric summary statistics will be presented instead.
 
For time-to-event variables, such as time to TVF, survival curves will be constructed using Kaplan-Meier estimates.

--	---

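### The thrombus item in the definition of optimal non-target treatment names the target lesion, so no item directly checks the freshly stented site for thrombus

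*Protocol*

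**What the plan says.** The Key Inclusion Criteria of the Protocol allow up to two lesions, "located in separate epicardial territories, one designated the target lesion and the other a non-target lesion". The non-target lesion is treated first with an approved drug-eluting stent, and the condition for going on is: "If uncomplicated and considered optimal as defined by below, the target lesion can then be treated".

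The definition that follows is headed "Optimal treatment of non-target lesion" and has four items:

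- a: less than 20% "residual stenosis by visual assessment"
- b: absence of dissection
- c: "no evidence of thrombus in the target lesion or vessel"
- d: TIMI 3 flow

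The same cell then says that the non-target lesion carries no further restrictions. Separately, the Key Exclusion Criteria rule out a patient if "The proximal target vessel or target lesion contains thrombus".

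**The concern.** The four items are meant to describe the result at the lesion just stented. Item c is the only one that names a lesion, and it names the other one. Read literally, the operator looks for thrombus in a vessel that has not yet been treated, and no written item asks about thrombus in the new stent.

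The list matters because it decides whether a two-lesion patient may go on to receive the investigational scaffold. A site that follows item c to the letter checks the wrong vessel. A site that silently corrects it applies a criterion different from the written one. Two-lesion patients could then be admitted on different rules at different sites, and some could proceed with visible thrombus in the first stent.

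**Working it through.** The Protocol gives no figure on this point to reproduce. The check sets the texts side by side and then enumerates cases.

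**Can item c be read as covering the stented site?**

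1. *Target lesion* is a designated term in this cell, opposed to *non-target lesion*. Using it for the lesion just stented contradicts that designation.
2. The Key Inclusion Criteria put the two lesions in separate epicardial territories, and the later bullet on non-target intervention requires a separate major epicardial vessel. Adding *or vessel* to *target lesion* therefore does not reach the non-target site.
3. Item a can only describe the stented lesion. At that moment the target is untreated and, under the target lesion criteria, must have a stenosis of at least 50%, so it could not meet a limit of less than 20%. Item d also fits the stented vessel, since target eligibility asks only for TIMI flow of 1 or more. Item c is the one that does not fit.
4. The cell places no further restrictions on the non-target lesion, so nothing else there supplies the missing check.

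**What do the other items catch?**

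Suppose there is visible thrombus at the non-target lesion, no dissection (item b met) and no thrombus in the target lesion or vessel (item c met as written). Cross residual stenosis with TIMI flow, counting thrombus that narrows the lumen as residual stenosis:

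| Residual stenosis | TIMI flow | Item a | Item d | All of a–d, as written | All of a–d, item c corrected |
|---|---|---|---|---|---|
| <20% | 3 | met | met | pass | fail (c) |
| <20% | below 3 | met | not met | fail | fail |
| ≥20% | 3 | not met | met | fail | fail |
| ≥20% | below 3 | not met | not met | fail | fail |

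As written, 1 of 4 cases passes; with item c naming the non-target lesion, 0 of 4 pass. If an operator does not count thrombus as residual stenosis, item a gives no protection and both TIMI 3 rows pass, which makes 2 of 4. These are counts of case types, not of patients, and they say nothing about how often each occurs.

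**What does item c add at the target?**

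The Key Exclusion Criteria already cover the target lesion and the proximal target vessel. As written, item c adds only the distal target vessel, and only in two-lesion patients.

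**Who could be affected?**

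The Enrollment row reports enrolment and follow-up of the 120-patient main cohort as complete. It describes the further arm prospectively: "The Low Profile 1 study arm is designed to enroll 100 non-randomized patients". The Protocol does not say how many of these 100 remain to be enrolled or how many will have a second lesion, so no patient number can be given.

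**The case against.** The strongest reply is that this is a drafting slip with almost no consequence. The heading tells the reader which lesion the list concerns, and an operator assessing a lesion just stented may well read item c as meaning that lesion. The procedure must also be uncomplicated, which would ordinarily exclude visible thrombus in a new stent. The remaining scenario needs an operator who sees thrombus and still calls the procedure uncomplicated. Nothing analytical depends on it either: "Only the target vessel will be evaluated for the key safety and efficacy endpoints".

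Much of this stands. The practical effect is small, no endpoint is touched, and the case counts have no frequency behind them. It also stands that a target check may have been intended, so a fix should not delete it.

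Two parts do not remove the point. Reading item c as the lesion just stented requires the reader to override a term the same cell designates. And *uncomplicated* is not defined in the Protocol, so it is an indirect safeguard that depends on judgement. Having written an explicit thrombus item, the plan should not have to rely on that word for the site the list is about.

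**Conclusion.** The point holds as a minor wording error in an operative eligibility criterion. No item in the definition directly tests for thrombus at the stented non-target lesion. The uncovered case is visible thrombus with less than 20% residual stenosis, TIMI 3 flow, no dissection and no target thrombus; it meets all four items and is stopped only if the operator judges the procedure complicated.

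The conclusion rests on the literal use of *target lesion* as the cell designates it. That only one case type is left open rests also on lumen-narrowing thrombus being counted as residual stenosis. No stated figure, endpoint, analysis population or analysis changes. The relevance is to the safety and consistent admission of two-lesion patients still to be enrolled, in a number the Protocol does not give.

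**What to change.** In item c, insert *non-target or* before *target lesion or vessel*, so that the thrombus check covers both sites. This is the wording to prefer: it closes the gap and keeps the distal target-vessel check that item c now provides in two-lesion patients.

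The alternative is to replace *target* with *non-target* in item c. Thrombus in the target lesion or proximal target vessel would stay excluded under the Key Exclusion Criteria, but the distal target-vessel check in two-lesion patients would be lost.

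Either way the cost is one reworded item, with no added procedure. No new exclusion line should be added, so that eligibility of single-lesion patients does not change.

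### The target-lesion length criterion names no arm and bars the lesions above 14 mm and up to 24 mm that the Low Profile 1 arm is described as enrolling

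*Protocol*

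**What the plan says.** All the text concerned is in the Clinical Study Summary of the Protocol.

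- **Key Inclusion Criteria, target lesion:** "length is ≤ 10mm or ≤ 14 mm and must be able to be covered by a single 14 mm or 18 mm" scaffold. Neither the criterion nor its heading names an arm. The same row makes all inclusion criteria compulsory for patient and lesion, and the Treatment Strategy row allows the target lesion to be treated only once they are met.
- **Enrollment, main cohort (120 patients):** lesions "≤ 10 mm or ≤ 14 mm in length able to be covered by a single 3.0 x 14, 3.0 x 18mm", followed by the other diameters in the same two lengths. The paragraph closes with "Enrollment and follow-up is complete".
- **Enrollment, LP1 arm (100 patients):** the upper length limit is given as "≤ 24 mm in length able to be covered by a single 3.0, 3.25 or 3.5 mm x 14, 18 or 28 mm", alongside a lower one of 10 mm. On timing it says that patients in this "Arm will be enrolled at select sites. Follow-up will conclude at the end of 3 years".
- **Clinical Study Design:** lesions of at most "14 mm in length, designated the target lesion, located in a native coronary artery", and then "All patients will receive a 3.0, 3.25 or 3.5 mm x 14, 18 or 28 mm scaffold".
- **Treatment Strategy:** "Target lesion length should be ≤ 10 mm or ≤ 24 mm by visual estimate", with at least 2 mm of healthy vessel on each side. Table 1 pairs lesions up to 10, 14 and 24 mm with scaffolds of 14, 18 and 28 mm. Again no arm is named.

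**The concern.** An eligibility criterion decides who enters an arm. Here the binding criterion and the arm description give opposite answers for the same patient. A site that follows the criterion turns away LP1 patients whom the arm was designed to include. A site that follows the LP1 paragraph or Table 1 enrols them against a compulsory inclusion criterion. The protocol does not say which text prevails, so the LP1 population is not uniquely defined.

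There is a possible knock-on effect for analysis. Endpoints are to be analysed in the modified intent-to-treat evaluable population, which excludes patients with major procedural protocol deviations. The protocol gives one example of such a deviation, a scaffold placed outside a native coronary artery. It does not say whether a lesion over the length limit counts.

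**Working it through.** There is no sample-size or power figure to reproduce. The check sets the length limits side by side and tests Table 1 against the protocol's own margin rule.

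**1. Limits as stated**

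| Place in the Protocol | Arm named | Lesion length | Scaffold length |
|---|---|---|---|
| Enrollment, first paragraph | main cohort | ≤ 10 or ≤ 14 mm | 14, 18 mm |
| Enrollment, LP1 paragraph | LP1 | ≤ 10 or ≤ 24 mm | 14, 18, 28 mm |
| Clinical Study Design | none | ≤ 14 mm | 14, 18, 28 mm |
| Treatment Strategy, length bullet | none | ≤ 10 or ≤ 24 mm | not stated |
| Treatment Strategy, Table 1 | none | ≤ 10, ≤ 14, ≤ 24 mm | 14, 18, 28 mm |
| Key Inclusion Criteria | none | ≤ 10 or ≤ 14 mm | 14, 18 mm |

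**2. Is the 24 mm / 28 mm class a slip?** With 2 mm of healthy vessel on each side, the longest lesion that a scaffold covers is its length minus 2 × 2 mm:

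- 14 − 4 = 10 mm
- 18 − 4 = 14 mm
- 28 − 4 = 24 mm

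All three rows of Table 1 reproduce exactly, and the 28 mm size also appears in the Clinical Study Device row. The third class is coherent with the rest of the table and does not look like a typing error.

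**3. Which rows does the inclusion criterion cover?** Only the first two. For a lesion above 14 mm and up to 24 mm, both halves of the criterion fail: the lesion exceeds 14 mm, and an 18 mm scaffold with the margins covers at most 14 mm. Read literally, the criterion leaves the 28 mm scaffold with no eligible lesion that needs it.

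**4. The Clinical Study Design row.** Its 14 mm lesion limit corresponds to the 18 mm scaffold, so the 28 mm scaffold it lists has no matching lesion length there. The same conflict sits inside one row.

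**5. Which arm does the criterion fit?** Its limits equal those of the main cohort, reported as complete. LP1 is the only arm that the text at hand words as still to be enrolled, and the criterion does not fit it. Elsewhere the protocol does separate the arms: clinical follow-up runs to 5 years for main-study patients and to 3 years for LP1. The length criterion makes no such distinction.

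This establishes the conflict. It does not show which limit is intended.

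**The case against.** The strongest reply is that the intended meaning is fairly plain. The longer lesion or scaffold appears in several rows, and the inclusion criterion repeats the completed cohort's limits, so it is probably wording that was not updated. That is a reasonable inference, but no text confirms it, confines the criterion to the main cohort or gives the LP1 paragraph precedence.

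The status of LP1 is also uncertain. The protocol keeps future wording for work it calls finished: it still says that main-trial patients will undergo follow-up. LP1 may already have been enrolled by this revision. In that case the defect concerns documentation and the classing of deviations more than future screening. This caveat stands, but the contradiction remains either way.

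Two limits of the text also stand. It is a summary listing key criteria, and its title names a CX arm that is not described further. Fuller criteria by arm may exist elsewhere, so the finding applies to the text at hand.

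Finally, the study is non-randomized and descriptive, the intent-to-treat population keeps every enrolled patient, and nothing classes excess lesion length as a major procedural deviation. No statistical figure changes. That is correct and bears on how serious the point is. It does not settle who is eligible.

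**Conclusion.** The concern holds. For an LP1 lesion above 14 mm and up to 24 mm, the protocol both admits the patient (LP1 paragraph, length bullet, Table 1) and bars the patient (inclusion criterion). The range is the 28 mm row of Table 1; LP1 lesions up to 14 mm are unaffected. LP1 plans 100 patients, but the share in that range cannot be derived from the document.

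Confidence is high that the text contradicts itself. The conclusion assumes only that the inclusion criteria bind every arm, as the protocol says without exception. It makes no assumption about which limit is intended or which text sites follow. Because a compulsory eligibility rule decides who enters the arm, this is more than a clerical slip and has to be corrected.

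**What to change.** Reconcile the Enrollment, Clinical Study Design, Treatment Strategy (with Table 1) and Key Inclusion Criteria rows so that each arm carries one lesion-length limit and one set of scaffold lengths, worded the same way throughout. The sponsor must decide the limit for each arm. If the present criterion is meant only for the completed main cohort, say so and give LP1 its own criterion.

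Once that is done, a lesion within its arm's reconciled limit is not by itself a protocol deviation. The other conditions for the evaluable population stay as they are.

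The cost is a protocol wording amendment and a matching screening form, with no extra patients or procedures.

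### The evaluable set excludes undefined bailout scaffolding while the only bailout provided is metal stenting, so it is unclear whether scaffold-plus-stent patients are in or out

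*Protocol*

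**What the plan says.** All places are in the Protocol's Clinical Study Summary.

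- **Statistical Analysis, Modified-Intent-to-Treat Evaluable Population.** The set holds "patients who have received the investigational device at the target lesion", with "no major procedural protocol deviations (e.g. scaffold implanted in a non-native coronary artery" as the kind of deviation meant, and with "no bailout scaffolding and for whom follow-up data is available". Bailout scaffolding is not defined here or elsewhere in the document.
- **Treatment Strategy.** The single rule on bailout reads "Bailout stenting should be conducted using any approved DES stent incorporating an “olimus” drug or bare metal stent". It does not mention a second DESolve scaffold.
- **Statistical Analyses.** "All clinical, angiographic, IVUS and OCT endpoints will be analyzed for the modified-intent-to-treat evaluable population". MSCT is not named. An intent-to-treat population covering every enrolled patient is also defined, but the document assigns no endpoint to it.
- **IVUS and OCT Endpoints.** These include scaffold area, change in scaffold and vessel size, and "Changes in strut appearance suggesting bioresorption".

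**The concern.** An exclusion from an analysis set has to name an event that the analyst can recognise in the data. Here the excluded event is a bailout by scaffold, and the bailout that the protocol provides is by metal stent. The patient in question received a DESolve scaffold and then a bailout DES or bare metal stent at the same lesion. Two analysts could classify this patient differently, and each could defend the choice from the text.

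The stake lies in what the endpoints measure. The imaging endpoints are meant to describe a device that resorbs. A permanent stent does not resorb, and it affects lumen size in its own way: a DES adds another drug and a bare metal stent adds none. The clinical endpoints are meant to capture the patient's course after an attempt with the study device, and a bailout is part of that course. One clause governs both kinds of endpoint, so either reading damages one of them.

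**Working it through.** The plan gives no figure to reproduce on this point: no bailout rate, no standard deviation and no sample size derivation. The check is mainly a comparison of texts.

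**Step 1. Which clause could remove a scaffold-plus-metal-stent patient?**

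| Clause of the evaluable set | Removes this patient? |
|---|---|
| Study device received at the target lesion | No, the scaffold was received |
| No major procedural deviation | Not plainly, because bailout by stent follows Treatment Strategy |
| No bailout scaffolding | Depends on the meaning of an undefined term |
| Follow-up available | No |

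A lesion treated with a metal stent *alone* fails the first clause and is out under any reading. The issue is confined to scaffold plus stent.

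**Step 2. How does the document use the two words?** It sometimes calls the DESolve device a stent. IVUS and OCT Endpoints speaks of "assessment of the lesion and stent morphology and stent strut composition over time", where Clinical Study Design says scaffold in the parallel sentence, and Table 1 heads the scaffold sizes as stent sizes. The reverse does not occur: metal devices are called drug eluting stent, DES or bare metal stent, never scaffold. In the disputed sentence itself, the scaffold in the deviation example is the study device.

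**Step 3. Does the literal reading have any content?** Yes. Enrollment and Key Inclusion Criteria require that one scaffold cover the lesion, so an unplanned second DESolve scaffold is a coherent meaning. The document does not, however, provide for such a bailout.

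**Step 4. What follows from each reading?**

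| Reading | Imaging endpoints | Clinical endpoints |
|---|---|---|
| Literal (second scaffold only) | Scaffold-plus-stent lesions included | Patients and their events included |
| Broad (any bailout stent or scaffold) | Such lesions removed | Patients and their events removed |

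The literal reading is unsuited to the left column and the broad reading to the right.

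**Step 5. Size, on assumptions.** Take a bailout rate p of 2% to 5% (assumed).

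- Patients affected, p × n: Low Profile 1 arm (n = 100), 2 to 5; main cohort (n = 120), 0.02 × 120 = 2.4 to 0.05 × 120 = 6.
- Literal reading, shift in mean late loss = p × d, where d = 0.5 mm is an assumed difference between bailout and other lesions: 0.02 × 0.5 = 0.010 mm to 0.05 × 0.5 = 0.025 mm. The direction depends on the bailout device.
- Imaging subset of 35: one such patient is 1/35 = 2.9% of the sample.
- Broad reading, weight of one lost event relative to all enrolled patients: 1/100 = 1.0 percentage point in the Low Profile 1 arm and 1/120 = 0.8 in the main cohort.

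**The case against.** The strongest reply is that the sponsor simply meant the bailout described under Treatment Strategy. The document is loose with stent and scaffold, that rule is its only bailout rule, and a clause should be read so that it has effect. On that view these patients are excluded, and the imaging endpoints are clean. This stands as a plausible account of intent. It does not settle the text, because the loose usage runs one way only and a second scaffold is a possible meaning. Nor does it end the matter, because the broad reading takes the same patients out of MACE, revascularization and scaffold thrombosis.

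A reader might go further the other way and infer that lesions rescued with metal do remain in the imaging results. The documents do not support that. No passage says so, the sponsor may have intended the opposite, no bailout is reported, and nothing describes where a bailout stent would lie relative to the scaffold.

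It can also be said that the study is observational and descriptive, with no test or threshold that a shift of 0.010 to 0.025 mm could overturn. That is correct and limits the weight of the point. Finally, detail on analysis sets often sits in the statistical analysis plan, which is not at hand and may define the term. The Protocol nevertheless writes this rule out itself, in words that do not match its own bailout provision.

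**Conclusion.** The point holds as an undefined and mismatched term in a rule that decides membership of the set used for all clinical, angiographic, IVUS and OCT endpoints. Contamination of the imaging endpoints is not demonstrated. It is the consequence of one reading, and loss of clinical events is the consequence of the other.

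The size is unknown. The figures above rest on an assumed bailout rate and an assumed late-loss difference, and they suggest a small effect on mean late loss. A single patient counts for more in the subset of 35 and, under the broad reading, in the event rates. The correction is worth making because it is cheap and improves the analysis whichever reading was meant. It concerns only who is analysed, not which device should be used for bailout.

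**What to change.** 1. Reconcile the population definition with Treatment Strategy. Suggested term: bailout with any additional stent or scaffold at the target lesion.
2. Apply this exclusion to the angiographic, IVUS and OCT endpoints only.
3. Keep bailout patients in the clinical endpoints and flag them by bailout device (DES, bare metal stent, second scaffold). One way is to report the clinical endpoints on the intent-to-treat population that the Protocol already defines.

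**Cost.** The text change is short. A few patients leave the imaging analyses, and clinical event rates may look slightly less favourable. Using the intent-to-treat population would also bring in patients who never received the scaffold or had major deviations, so the sponsor should state that this is intended. The flag needs the bailout device to be on record for each patient, which the document does not show. Enrollment states that follow-up of the main cohort is complete, so for those 120 patients the change should be labelled as made after data collection.
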